### 7.4 M0 Phase Imaging Visits

This visit occurs if the investigator determines that imaging study(ies) is/are needed to assess development of metastatic disease (M1 CRPC) and the imaging occurs  $>$  1 month after baseline or more than 1 month before or after a 6-month M0 Phase study visit. The following will occur during the visit:

- ECOG performance status.
- Current opioid analgesic use (yes/no).

- Pain status (with BPI).
- Prostate cancer interventions as described in Section [7.6.13](#)
- Survival status as described in Section [7.6.14](#).
- Bone and soft tissue imaging studies for detection of metastatic prostate cancer.
- Blood sample for clinical laboratory tests at local laboratory, as indicated in the Schedule of Assessments ([Table 1](#)).
- Serious adverse events in patients who receive at least 1 partial ( $> 0$  mL) infusion of Provenge that occur  $\leq$  30 days after the last infusion, regardless of relationship to Provenge.
- Blood sample for biomarker analysis (within  $\pm 1$  month of imaging), providing the patient has consented to AOR.

Any imaging study that occurs within 1 month of a 6-month M0 Phase study visit will be considered part of that 6-month M0 Phase study visit, and no repeat assessments will be required.

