### **7.6.15 Imaging Studies**

Patients will undergo bone imaging studies (e.g., MRI,  $^{99m}\text{Tc}$  bone scintigraphy or  $^{18}\text{F-NaF}$  PET/CT) and soft tissue imaging studies (e.g., contrast-enhanced abdominal and pelvic CT or MRI) at the baseline visit and M0 Phase visits in order to detect any M1 disease. The imaging modality will be determined based on the study site’s standard of care and will be recorded on the eCRF.

The presence of M1 disease will be determined by the presence of bone, regional or distant nodal, or visceral metastasis, as follows:

- **Bone metastasis**

Patients with one or more unequivocal bone lesions as identified by site’s standard for imaging modality will be considered to have M1 CRPC. Patients with equivocal scans determined by standard imaging (e.g.,  $^{99m}\text{Tc}$  bone scan) will be evaluated by more sensitive imaging modalities such as CT,  $^{18}\text{F-NaF}$  PET/CT, or MRI within 1 month of the equivocal scan to confirm M1 disease status ([Adams 2011](#)).

- Regional or distant nodal metastasis

Patients diagnosed with lymph node(s) (measuring  $\geq 2$  cm on the greatest diameter) in either regional pelvic or distant lymph nodes will be considered to have M1 disease (Scher 2008).

Examples of regional lymph nodes include: hypogastric, obturator, internal and external iliac and lateral, presacral and promontory sacral lymph nodes (Adams 2011).

Examples of distant lymph nodes, which lie above the bifurcation of the common iliac arteries and outside of the confines of the true pelvis, include: aortic, common iliac, deep inguinal, superficial inguinal, supraclavicular, cervical, scalene, and retroperitoneal lymph nodes (Adams 2011).

- Visceral metastasis

Patients diagnosed with metastasis to liver, lung, brain, or other solid organ will be considered to have M1 disease.

The number and sites of bone, regional or distant nodal, or visceral metastases, if present, will be recorded on the eCRF.

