The same bone and soft tissue imaging modalities utilized at baseline should be used for all images for a given patient until diagnosis of M1 CRPC. However, the imaging modality may be changed at the investigator's discretion, assuming that subsequent imaging studies are performed with the new modality. If the diagnosis of M1 CRPC occurs during the first use of a new imaging modality (e.g., first use of  $^{18}\text{F}$ -NaF PET/CT imaging after previous use of  $^{99\text{m}}\text{Tc}$  bone scintigraphy), an additional imaging study with the previous imaging modality will be performed within 1 month after the positive imaging study to allow comparison of the sensitivity and specificity of the 2 methods; this additional imaging study will be reimbursed by the sponsor. However, if the change is from a higher to a lower sensitivity modality, the higher sensitivity modality will not be repeated.

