### **8.3.2 Secondary Endpoints**

The proportion of patients who receive a diagnosis of M1 CRPC at the time of the baseline imaging study will be categorized as metastatic due to soft tissue (nodal and/or visceral) metastases, bone metastases, or both. The percentage of patients in each category will be computed based on the primary analysis population.

Logistic regression analyses, similar to the analyses described for the primary endpoint, will be used to identify characteristics predictive of an imaging study positive for M1 in the M0 population. Analyses will be performed using baseline information only as predictor variables with the outcome variable as a positive imaging study (yes/no) at any post-baseline time point. In addition, an analysis will be performed on the M0 population using all imaging studies collected in the study as the outcome variable (positive=yes/negative=no) with predictor variables associated with each imaging study. Appropriate methods accounting for the correlation of multiple studies for a patient, such as generalized estimating equations, will be used for this analysis. Cox regression analyses incorporating information on the time to occurrence of a positive imaging study will be performed to supplement these analyses.

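### The image-level secondary analysis does not define its unit, so discordant scans from one occasion and a repeat scan after diagnosis can enter as separate yes/no outcomes

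*Combined protocol and SAP*

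**What the plan says.** Section 8.3.2 gives the M0 population a patient-level logistic model (any positive post-baseline study), supplementary Cox models, and an image-level model "using all imaging studies collected in the study as the outcome variable (positive=yes/negative=no) with predictor variables associated with each imaging study". On several studies from one man it says only: "Appropriate methods accounting for the correlation of multiple studies for a patient, such as generalized estimating equations, will be used for this analysis". It gives no rule for combining studies from the same occasion.

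The term is used in two ways:

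- **One scan.** Section 7.6.15 has patients undergo bone imaging studies "and soft tissue imaging studies (e.g., contrast-enhanced abdominal and pelvic CT or MRI) at the baseline visit and M0 Phase visits". If M1 is found at first use of a new modality, "an additional imaging study with the previous imaging modality will be performed within 1 month after the positive imaging study", unless the change was to a less sensitive modality. Section 7.4 lists, for an imaging visit, "Bone and soft tissue imaging studies for detection of metastatic prostate cancer".
- **The whole work-up.** The first paragraph of section 8.3.2 says that M1 found at the "baseline imaging study will be categorized as metastatic due to soft tissue (nodal and/or visceral) metastases, bone metastases, or both", so a single study can cover both compartments. The primary endpoint in section 8.3.1 is worded in the same way.

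The patient's status follows an any-site rule: "The presence of M1 disease will be determined by the presence of bone, regional or distant nodal, or visceral metastasis" (section 7.6.15). Modality depends on the site's "standard of care and will be recorded on the eCRF", but it is not among the candidate predictors in section 8.3.1. The document closes by stating that the SAP was not finalized, so nothing later settles the unit.

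**The concern.** The secondary objective is to find what predicts future M1 in a patient. If each scan is an outcome, the model estimates the probability that a scan is positive. That differs from the probability that a man has M1 when imaged whenever bone and soft tissue results disagree. ECOG status, opioid use, pain scores and laboratory values are collected per visit (sections 7.3 and 7.4), so two scans from one visit would share them and differ only in outcome.

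The previous-modality repeat is a separate problem. It is triggered by a positive result and follows the diagnosis. If the older modality is negative, a man just diagnosed with M1 contributes a negative record. The number of records per man then depends on the outcome.

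Section 8.3.2 describes these analyses as similar to the primary one, which is to yield a formula for predicted probability. Section 1.2 says the data should inform the timing and utility of imaging. A probability that is too low for the decision at hand therefore matters more than a modest shift in an odds ratio.

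**Working it through.** **The plan's own figure.** Section 8.1 gives none for this model. Its figures for the primary endpoint reproduce: 34.95% versus 29.05% gives an odds ratio of 1.312, and 1000 per level gives 80.8% power (981 per level needed). They are at patient level and neither support nor refute this point.

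**Assumptions (none stated in the documents).** Each occasion has one bone and one soft tissue scan. A share d = 0.80 to 0.85 of positive occasions is positive on one scan only, so f = 1 - d = 0.15 to 0.20 is positive on both. The occasion rate is p = 20%.

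**Predicted probability.** Per-scan rate = p(1 - d/2).
- d = 0.80: 0.20 × 0.600 = 12.0%.
- d = 0.85: 0.20 × 0.575 = 11.5%.

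The fall from 20% is 40% to 42.5%.

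**A predictor acting on both compartments.** Take 30% versus 15% per occasion.
- Per occasion: (0.30/0.70)/(0.15/0.85) = 2.43.
- Per scan, d = 0.80: 18% versus 9%, (0.18/0.82)/(0.09/0.91) = 2.22.
- Per scan, d = 0.85: 17.25% versus 8.625%, odds ratio 2.21.

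**A predictor acting on bone only.** At the reference level take bone 12% and soft tissue 6%, with a bone odds ratio of 3.0. Bone odds become 3 × 0.12/0.88 = 0.409, or 29.0%.
- Per scan: (29.0% + 6%)/2 = 17.5% versus (12% + 6%)/2 = 9%, odds ratio 2.15.
- Per occasion, independent sites: 1 - 0.710 × 0.94 = 33.3% versus 1 - 0.88 × 0.94 = 17.3%, odds ratio 2.39.
- Per occasion, a share f positive on both: any-site rate = (bone + soft tissue)/(1 + f). For f = 0.15, 30.5% versus 15.7%, odds ratio 2.36. For f = 0.20, 29.2% versus 15.0%, odds ratio 2.34.

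The contrast is therefore 2.15 against 2.34-2.39.

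**The protocol's rates borrowed as occasion rates** (34.95% and 29.05%, mean 32%):

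| d | mean per-scan rate | odds ratio |
|---|---|---|
| 0 | 32% | 1.312 |
| 0.25 | 28% | 1.293 |
| 0.50 | 24% | 1.275 |
| 0.75 | 20% | 1.260 |
| 1 | 16% | 1.246 |

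**Does GEE repair it?** In a simulated set of 20,000 men with d = 0.50, independence and exchangeable GEE both gave an odds ratio of 1.234 and a reference-level probability of 22.3%. Logistic regression on the any-site occasion outcome in the same data gave 1.255 and 29.7%.

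**Fewer two-scan occasions.** Suppose half the occasions have a single scan, positive at the occasion rate. Positives per record are then p[0.5 + 0.5(2 - d)]/1.5. With p = 20% this is 14.7% for d = 0.80 and 14.3% for d = 0.85. The 2.43 becomes 2.28 and 2.27.

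**Repeat and equivocal scans.** No frequencies are given, so no size can be attached. Section 7.6.15 sends equivocal bone scans for further imaging within 1 month, but no rule says how an equivocal scan is coded yes or no as its own record.

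**The case against.** The strongest reply is that the scan-level unit is one reading of an ambiguous term. A reader might infer that the plan certainly counts each scan separately. The documents do not support that: section 8.3.2 itself uses the singular for a work-up that can show either compartment or both, and on that usage the bone-positive, soft-tissue-negative man is one positive record. A reader might also infer that same-occasion scans carry identical predictors. Predictors for this model are not listed, section 8.3.1 allows the candidate list to change, and modality could be added. Two scans per occasion is likewise an assumption: M0 Phase imaging is as needed, and MRI is named for both compartments.

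All of this stands, and it limits the point to what the wording permits. It does not remove it. Two usages within one section leave the programmer to choose. The work-up reading also does not deal with the previous-modality repeat, which section 7.6.15 calls an imaging study in its own right. Sections 7.3 and 7.4 fold imaging within 1 month of a 6-month visit into that visit, but they do not say how results combine, and they do not reach a repeat done after an imaging visit between scheduled visits.

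It is also fair that this is an additional secondary analysis beside a patient-level model that does not depend on scan counts.

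**Conclusion.** The concern holds in a limited form. The unit of the image-level model is undefined. Under the scan-level usage, discordant scans from one occasion enter as opposing outcomes. Under either usage, a post-diagnosis repeat can enter as a further record. GEE does not correct either problem.

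Under the assumptions above, the predicted probability falls by about 40%, and less if many occasions have one scan. Odds ratios move modestly: 2.43 to about 2.21, or 2.34-2.39 to 2.15 for a bone-only predictor. Two stronger readings are tempting and wrong. Probabilities are not halved at these discordance shares; that would need every positive occasion to be positive on one scan only. Nor is 3.0 to 2.15 the loss for a bone-only predictor, because an any-site occasion outcome also dilutes a bone-only effect.

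The primary analysis and the patient-level analysis of any positive post-baseline study are unaffected. The change should be made, but it does not threaten the study's main conclusion.

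**What to change.** In section 8.3.2, and in any SAP that is completed:

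- Define the unit as the imaging occasion: all bone, soft tissue and confirmatory studies within 1 month of each other. Sections 7.3, 7.4 and 7.6.15 already use a 1-month window.
- Call the occasion positive if any study in it meets the M1 criteria of section 7.6.15. An equivocal scan then takes the result of its work-up.
- Exclude the post-diagnosis previous-modality repeat from this model. Keep it for the comparison of modalities, its stated purpose in section 7.6.15.
- Keep GEE or a similar method for repeated occasions within a man.
- As support, model bone positivity and soft tissue positivity as two separate outcomes.

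The cost is wording and programming. Modality and the number and sites of metastases are already recorded, and study dates are needed for the Cox analyses in any case. The downside is fewer records, with no loss of patients or M1 diagnoses.

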### **8.3.3 Exploratory Endpoints**

Prostate cancer treatment practice patterns will be summarized descriptively for patients with M0 CRPC and M1 CRPC. Prostate cancer interventions prior to study entry will be summarized. Additionally, the timing and sequence of prostate cancer interventions during the study will be summarized.

The identification of biomarkers in the M0 population that are predictive of an imaging study positive for M1 will be performed using logistic regression and Cox regression, as previously described. These analyses will be performed for both the primary endpoint (a positive imaging study at baseline) and the endpoint of a positive imaging study at any post-baseline time point.

The percentage of patients with CRPC with previously undiagnosed M1 at baseline will be calculated as 100 times the number of patients in the M1 analysis population divided by the total number of patients in the study.

Logistic regression analyses will be used to determine patient characteristics in the M0 population that are predictive of a positive imaging study at baseline as detected with different imaging modalities. The differing imaging modalities include MRI, 99mTc bone scintigraphy, or F-NaF PET/CT for bone imaging; and contrast-enhanced abdominal and pelvic CT or MRI for soft tissue imaging. For each imaging modality, multivariate logistic regression modeling will be used to identify factors that are independently predictive of a positive imaging study. These analyses will be performed for both the primary endpoint (a positive imaging study at baseline) and for the endpoint of a positive imaging study at any post-baseline time point.

Metastasis-free survival will be defined as time from the date of the baseline imaging study to the first occurrence of M1 or death due to any cause in the M0 population. Patients who are not observed to develop M1 or who do not die will be censored at the last time observed for determination of M1. Only patients who are confirmed with M0 CRPC at study entry will be included in the analysis. Cox regression analyses will be used to analyze the MFS endpoint. Univariate Cox regression analyses will be performed separately for each baseline variable of interest. A multivariate Cox regression analysis will be performed including all baseline variables of interest. Various model selection procedures will be investigated, including forward, backward, and stepwise regression to identify a model that includes explanatory factors that are independently predictive of development of M1 or death. Supplementary analyses, including time-varying covariates of ECOG performance status and laboratory parameters, will also be provided.

Overall survival will be defined as the time from diagnosis with M1 CRPC until death. Patients who do not die will be censored at the last date they were known to be alive. Analyses similar to those described for MFS will be performed in the M1 population to determine patient characteristics that can be used to predict OS. The Kaplan-Meier method will be used to quantify the survival duration from the time of diagnosis with M1 CRPC. In addition, the effect of prostate cancer interventions and their sequencing on OS will be evaluated using a Cox regression analysis with time-varying covariates.

The timing and sequence of prostate cancer interventions will be summarized descriptively for the M1 population. The time to prostate cancer interventions will be defined as the time from the date of diagnosis with M1 CRPC until initiation of the prostate cancer intervention.

Changes in serum PSA levels during treatment for M1 CRPC will be summarized descriptively for the M1 population. For treatments with sufficient patient numbers, changes in serum PSA levels over time, PSA progression, and PSA progression-free survival will be

summarized descriptively by treatment. The maximum percentage reduction in serum PSA levels will also be summarized descriptively by treatment.

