#### **7.6.17 Additional Optional Research for Biomarkers**

Patients will be given the opportunity to consent to allow Dendreon to collect investigational blood samples for use in AOR, which will include biomarker analysis and other additional testing. The samples will be analyzed for biomarkers that may be predictive of treatment effects and/or prognostic for MFS, OS, or an imaging study positive for metastatic disease. The samples will be retained for an indefinite period of time. They may be used for gene and gene expression analysis, and retained samples may be sent to outside laboratories for testing. Retained samples will be used for research only, and will not be sold. AOR blood samples will not be identified using patient names or other personal identifiers. Neither the patient nor the study site will receive AOR testing results.

For patients who provide consent for AOR, a whole blood sample will be obtained at the baseline visit and each M0 Phase visit (at scheduled 6-month M0 Phase study visits and M0 Phase imaging visits [within  $\pm$  1 month]) until diagnosis with M1 CRPC, or the M0 Phase patient completes or is discontinued from the study. Such samples will not be collected from patients who do not provide additional consent for AOR.

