#### **8.2.2 Interim Analysis**

No formal interim analysis is planned for this study. Periodic summarization of the data will be performed on an ongoing basis. However, as there are no formal hypotheses being tested in this protocol, no significance-level adjustments will be made for statistical testing or estimation procedures that may be utilized.

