The above list of variables will be considered for inclusion in the final model; however, each variable will be initially screened and will be dropped from consideration for inclusion in the final model if it is shown to have little predictive value as a univariate predictor. Candidate variables for the final model will be determined by the following algorithm. A univariate logistic regression will be applied for each individual variable and all variables with  $p < 0.25$  will be considered as candidate variables for the final model. Interaction terms will also be considered for the final model. Interaction terms will be considered as candidates for the final model if the  $p$ -value for the interaction term is less than 0.25 from a model with predictor variables of variable a, variable b, and interaction of variable a and b. Only variables with  $p < 0.25$  from the univariate model screening procedure as discussed above will be considered for determining the list of interaction terms for consideration in the final model.

All candidate variables, including interaction terms identified by the algorithm discussed above, will be entered into the stepwise model selection procedure. The criteria for a variable to enter the model will be  $p < 0.05$  and variables will be retained in the model during the elimination step if  $p < 0.10$ . The final model will include all terms identified from the stepwise selection procedure and will also include all main effect terms for any interaction variables identified in the stepwise model selection procedure.

Although the above list of variables for consideration for inclusion in the model is a comprehensive one, addition or deletion of variables for consideration may occur. Therefore, the complete list of candidate variables for inclusion in the model will be provided in the final statistical analysis plan.

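### Section 8.3.3 gives gene-expression biomarkers no selection method suited to a large panel: if few candidates are truly predictive, most selected markers would be expected to be false

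*Combined protocol and SAP*

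**What the plan says.** Two exploratory objectives (section 3.3) concern biomarkers: those predictive of M1 at baseline, and those predictive of later M1 in men who are M0 at baseline. The material is whole blood from men who consent to the optional research. Of the samples, section 7.6.17 says "They may be used for gene and gene expression analysis", and section 1.2 gives gene-expression profiling as the reason for collecting them. Neither section states a number of markers or a platform.

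For the method, section 8.3.3 says only that the work "will be performed using logistic regression and Cox regression, as previously described". Looking back, section 8.3.1 is the one place with a complete selection rule:

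- "A univariate logistic regression will be applied for each individual variable", and those with p<0.25 become candidates.
- "Interaction terms will also be considered for the final model", pairwise among the screened variables, again at p<0.25.
- "The criteria for a variable to enter the model will be" p<0.05, and "variables will be retained in the model during the elimination step if" p<0.10.

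Section 8.3.1 also asks for one multivariate model with every variable of interest. Section 8.3.2 mentions Cox models but gives no selection rule for them.

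Section 8.2.2 states that "no significance-level adjustments will be made for statistical testing or estimation procedures that may be utilized". It stands under the interim analysis heading, but its wording covers all testing and estimation. The candidate list was left to the final SAP, and the closing note says that the SAP was not finalized. Section 8.3.3 places the biomarker work, including the baseline-M1 endpoint, in the M0 population.

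**The concern.** The section 8.3.1 rule was built for a short list of clinical variables. Its screen is deliberately loose, it opens the door to pairwise interactions, and it has no error control beyond a 0.05 entry threshold. Gene-expression data can have hundreds or thousands of candidates. On that scale a loose screen with stepwise selection picks up many chance associations, and a model judged on the data that selected it looks far better than it is.

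At stake are both biomarker objectives, and the use made of blood drawn at baseline and at every M0 visit from consenting men. A reader of the results could not tell a real signature from noise. Section 1.2 also motivates the research by the prospect that biomarkers predict better than PSA and PSA doubling time, yet section 8.3.3 names no measure of that gain.

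**Working it through.** **Inputs.** From the protocol: 2000 patients; 32% expected M1-positive, so 0.32 × 2000 = 640 events; two-sided alpha 0.05; thresholds 0.25, 0.05 and 0.10. The list in section 8.3.1 has 26 variables (22 clinical items plus 4 pain scores). Assumed, because the documents do not say: the number of markers K, the share π truly predictive, and independence between markers. Biomarker data on all 2000 men is the best case, since consent is optional.

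**The plan's own figure.** Odds ratio = (0.3495/0.6505)/(0.2905/0.7095) = 1.312, as stated. With 1000 per level and a pooled proportion of 0.32, the null standard error is √(2 × 0.32 × 0.68/1000) = 0.02086 and the alternative standard error is 0.02082. Then z = (0.059 − 1.96 × 0.02086)/0.02082 = 0.87, giving 80.8% power. The figure reproduces, for one pre-named variable.

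**All markers null.** Passing the screen: s = 0.25K. Reaching p<0.05: 0.05K. Pairs examined: s(s−1)/2. Chance of at least one p<0.05: 1 − 0.95^K.

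| K | pass p<0.25 | p<0.05 | pairs | at least one |
|---|---|---|---|---|
| 50 | 12.5 | 2.5 | about 72 | 92% |
| 500 | 125 | 25 | 7,750 | >99.99% |
| 5000 | 1,250 | 250 | about 780,000 | >99.99% |

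At K=500, a quarter of the pairs (about 1,938) become interaction candidates. With the 125 main effects that makes about 2,063 candidates, more than the 2000 patients.

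**When false markers are the majority.** For main effects at 80% power, false outnumber true when 0.05(1−π) > 0.80π, that is π < 0.05/0.85 = 5.9%. Example: K=5000 with 100 true (2%) gives 0.05 × 4900 = 245 false against 0.80 × 100 = 80 true, so 245/325 = 75% false. Lower power raises the break-even: at 50% power it is 0.05/0.55 = 9.1%.

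**Simulating the section 8.3.1 rule.** Settings: n=2000, independent 50:50 binary markers, 32% positive, true markers at odds ratio 1.312, linear-probability approximation to the logistic tests. Mean share of selected markers that are false:

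| Candidates, true | main effects only | with interactions |
|---|---|---|
| 24, 12 | 6% | 13% |
| 24, 5 | 17% | 30% |
| 100, 50 | 7% | 20% |
| 100, 10 | 38% | 66% |
| 100, 5 | 52% | 82% |
| 1000, 100 | 42% | not run |
| 1000, 20 | 80% | not run |

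There were 25 to 200 replicates for 24 and 100 candidates, and 5 to 10 for 1000. With interactions the break-even lies above 6%: at 10% true in a panel of 100, two thirds of the selections are false.

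**Fitting and apparent discrimination.** For null, independent Gaussian markers with 32% positive, the all-variables logistic model becomes perfectly separable at about 0.46 markers per patient, or about 915 markers for 2000 men. Stepwise selection on noise alone (main effects, n=2000, one run per setting) gave 26 selected and an apparent AUC of 0.66 from 500 markers, and 323 selected and an AUC of 0.98 from 5000. The true AUC is 0.50 in both.

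**Population.** Section 8.2.1 defines the M0 population as men who are M0 at baseline. It contains no baseline positives, so the baseline-M1 biomarker model cannot be fitted there.

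**Price of strict control.** Bonferroni over 100, 1000 or 20,000 markers cuts power for odds ratio 1.312 from 81% to 26%, 11% or 3%. That favours false discovery rate control for discovery work.

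**The case against.** The strongest reply is that the work is labelled exploratory, rests on optional samples, and comes with an explicit statement that no formal hypotheses are tested. The back-reference may mean only the two regression families: the section 8.3.1 algorithm is worded for its own list of clinical variables, and section 7.6.17 says only that gene analysis is possible. Detail could have followed in the SAP.

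Much of this stands as a limit on the claim. Applying the full rule to biomarkers is a reasonable reading, not an explicit instruction. Exploratory status excuses the lack of confirmatory alpha control. It does not excuse a method that can return an AUC near 1 from noise, and no finalized SAP supplies another method.

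Three stronger readings are tempting, and the documents support none of them:

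- That the plan will yield mostly false markers. This needs K and π, and neither is given. Under the same rule the simulated false share runs from 13% to 82%. The all-null counts cannot settle it, because there every selection is false by construction.
- That separation sets in once markers exceed the roughly 640 events. In the null Gaussian case the threshold is about 915, and panels of 50 or 500 lie well below either number.
- That markers would never be set against PSA and PSA doubling time. If the section 8.3.1 procedure is carried over, both are on its candidate list. What is missing is a rule that keeps them in the model and a measure of the gain.

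**Conclusion.** The concern holds in conditional form. The plan sets no multiplicity control, no selection method suited to high dimension and no validation for gene-expression markers. If the section 8.3.1 rule is applied to a large panel with few true markers (below about 6% for main effects at 80% power, higher with interactions or fewer consenting men), most selected markers would be expected to be false. With thousands of markers the all-variables model cannot be fitted reliably and the selected model's apparent discrimination would be badly optimistic. A small panel rich in true markers would be much less affected: 13% false with 24 candidates, half of them true. These figures assume independent markers and data on all 2000 men.

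The misplaced population for the baseline-M1 analysis is a separate defect in the same paragraph and depends on none of these assumptions. The point is worth correcting, but it touches exploratory objectives only and leaves the primary analysis alone.

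**What to change.** In section 8.3.3, replace the back-reference for biomarkers with:

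1. Test each marker added to the final clinical model, with PSA and PSA doubling time included. Report the Benjamini-Hochberg false discovery rate, for example flagging markers below 10%. Exempt this analysis from the no-adjustment sentence in section 8.2.2.
2. Run no pairwise interaction screen among markers.
3. Build any multi-marker score with a penalised method such as elastic net, with all selection and tuning inside cross-validation. Report the cross-validated gain in AUC over the clinical model.
4. Run the baseline-M1 biomarker analysis in the men of the primary analysis population who gave optional research samples. Keep the M0 population for the future-M1 analysis.

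Other penalised methods and false discovery thresholds would also serve, provided they are fixed before the marker data are seen. The cost is analysis-plan text and a little more computing, with no change to visits, samples or data collection. The downside is that fewer markers will be declared.
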